STATISTICAL

ANALYSIS PLAN

Safety and efficacy assessment of deoxycholic acid (Embella[®]) injectable solution for the reduction of unwanted submental fat

NCT Number: NCT06509438

Date: November 20, 2022

STATISTICAL ANALYSIS PLAN

Name of Test Drug:	Embella®
Methodology:	Interventional, single-armed
Sponsor:	Espad Pharmed Darou Company
	Office:
	Espad Pharmed, [name]
	[contact]
Sponsor Representatives:	Zist Orchid Pharmed Co.
Statistical Analysis Plan Date:	November 20, 2022
Statistical Analysis Plan Version:	Version 1.0

Contents

Participate timeline	4
Section 1: Administrative information	5
Title and Trial registration.....	5
Trial registration number	5
SAP Version (SAP version number with dates)	5
Section 2: Introduction	5
Objectives.....	5
Primary objective(s):	5
Secondary objective(s):	5
Section 3: Trial Methods	5
Trial design – description of trial design	5
Inclusion Criteria	6
Exclusion Criteria	6
Withdrawal of Subjects	6
Randomization.....	7
Sample size	7
Section 4: Outcome Variables	7
Endpoints.....	7
Primary Endpoint.....	7
Secondary Endpoints	8
Safety End point	8
Section 5: Statistical analysis	10
Patient Characteristics and Baseline Comparisons.....	10
Primary and Secondary Endpoint Analysis	10
Safety Analysis.....	10
List and describe each primary and secondary outcome including details of: methods used for assumptions to	

be checked for statistical methods.....	11
Missing Data.....	11
Covariate Adjustment.....	11
Statistical Software.....	11

Participate timeline

Visit No	0	1	2	3	4	5	6
	Day 1						
Time	Baseline	Injection 1	Week 4 (± 2 days) (Injection 2)/ Follow-up of subjects with a satisfactory response who do not require further treatment	Week 8 (± 4 days) (Injection 3)/ Follow-up of subjects with a satisfactory response who do not require further treatment	Week 12 ± 4 day	Week 16 ± 4 day (In subjects with 2 injections)	Week 20 ± 4 day (In subjects with 3 injections)
Screening	X						
eligibility control	X						
Consent	X						
Demographic data	X						
Injection		X	X	X			
Pain assessment		X	X	X			
Digital Photography	X		X	X	X	X	X
Measurement of submental fat	X		X	X	X	X	X
Patients' satisfaction			X	X	X	X	X
Physicians' assessment According to SMF	X		X	X	X	X	X
Adverse Events	X	X	X	X	X	X	X

Section 1: Administrative information

Title and Trial registration

Evaluation of safety and efficacy assessment of deoxycholic acid (Embella®) (manufactured by Espad Darou Pharmed Company) for the reduction of unwanted submental fat

Trial registration number

IRCT20190210042676N29

SAP Version (SAP version number with dates)

Version: 1.0, Date: November 20, 2022

Section 2: Introduction

Objectives

Primary objective(s):

Safety and efficacy assessment of Embella® injectable solution in reducing the unwanted submental fat.

Secondary objective(s):

- Assessment of the efficacy of Embella® injectable solution, in improving the standard grading of submental fat (SMF)
- Assessment of the efficacy of Embella® injectable solution in reducing the diameter of submental fat
- Patient's satisfaction with the treatment process
- Pain assessment during the injection using a 11-point visual analogue scale
- Safety assessment of Embella® injectable solution

Section 3: Trial Methods

Trial design – description of trial design

It is a single group, before and after clinical study

Inclusion Criteria

- Age between 18 and 65 years old
- Individuals with any severity of unwanted submental fat
- Voluntarily signed the informed consent form and consented to the 3-month follow-up
- Willing to actively participate in the study and the scheduled visits

Exclusion Criteria

- Any previous interventions to treat SMF
- Anatomical features or previous trauma in the injection site which is liable to interfere with SMF evaluation or result in an aesthetically unacceptable outcome after treatment
- Evidence of any cause of submental enlargement other than SMF
- Patients with a body mass index (BMI) $> 30 \text{ kg m}^2$
- Those undergoing or considering a weight-reduction program
- Patients with a history of sensitivity to any components of the study medication or topical or local anesthetics
- Patients with a history of dysphagia
- Any inflammation, active infection, unhealed wound, or tissue scar at injection site
- Those using anticoagulants or NSAID or other medications that increase the risk of coagulation disorders within 7 days before injection
- Unrealistic expectations
- Pregnant or lactating women
- Those undergoing low sodium diets like hypertensive patients

Withdrawal of Subjects

- The patients were allowed and free to refuse to cooperate with the study and follow-up whenever they want, but the researchers try to collect the maximum information, including the reasons for leaving the study and, if possible, the final results of the treatment.
- If a patient missed 2 or more consecutively scheduled visits, he/she was dismissed from the study.
- Occurrence of any of the exclusion criteria
- Occurrence of serious adverse event (SAE).

Randomization

Since this is a single-group study, randomization is not applicable.

Sample size

This study will be conducted in 20 eligible participants.

Section 4: Outcome Variables

Endpoints

Primary and secondary endpoints are evaluated before injection and 4 and 12 weeks after the last injection.

Primary Endpoint

At least one-grade improvement in standard grading of submental fat (SMF) evaluated at 4 and 12 weeks after the last injection (Figure1).

Figure 1: Standard grading of submental fat (SMF)

Scale	0	1	2	3	4
Submental Convexity	Absent	Mild	Moderate	Severe	Extreme
Description	No localized submental fat evident	Minimal localized submental fat	Prominent localized submental fat	Marked localized submental fat	Extreme submental convexity
Representative Photographs					

Secondary Endpoints

- Submental fat diameter will be measured with the calliper at 4 and 12 weeks after the last injection
- Intensity of procedural pain will be assessed using the Visual Analogue Scale (VAS), ranges from 0 (complete painlessness) to 10 (maximum pain).
- Patient satisfaction will be assessed using the Visual Analogue Scale (VAS), ranges from 0 (not satisfied at all) to 10 (maximum satisfaction).
- Any observed or reported adverse events will be recorded after the injections and at 4- and 12-weeks follow-up visits, graded as mild [1] moderate [2] and severe [3].

Safety End point

Assessment of Adverse Events.

Adverse Event (AE) is described as any medical event that occurs in patients participating in a study, which differs from the clinical manifestations of the underlying disease progression and does not necessarily have a causal relationship with the treatment used in the study. Clinical manifestations that will be reported as adverse events include any symptoms, signs (such as any abnormal laboratory results), or temporary illness related to the use of the product being studied, whether or not these effects are causally related to the product under study.

Very common adverse events of DCA include:

- Pain
- Edema
- Numbness, tingling,
- Swelling
- Bruising
- Redness of the skin (erythema)
- Itching

Common adverse events of DCA include:

- Injection site reaction
- Bleeding
- Pain and discomfort

- Flushing
- Change of skin color
- Nerve injury around the jaw
- Skin tightness
- Difficulties in swallowing (dysphagia)
- Feeling sick (nausea)
- Headache

Uncommon adverse events of DCA include:

- Unusual taste in the mouth
- Difficulties in speaking
- Hair loss (alopecia)
- Hives (urticarial)
- Skin sores (ulcer)
- Scar

Adverse events of DCA where the frequency is not known include (frequency cannot be estimated from the available data) :

- Reduced or abnormal sensation in the area of the mouth (e.g. lip, tongue)
- Reduced sense of touch or altered sensation in the cheek
- Tissue damage and cell-death (necrosis) around the treatment area
- Injury of blood vessels if injected accidentally into artery or vein

The medical conditions that existed prior to the start of the study are only considered as adverse events if they have worsened during the course of the study and cannot be attributed to the natural progression of the disease.

Serious Adverse Reaction (SAR) is described as a harmful response to an intervention and includes:

•result in death.

•pose a risk of death.

•require hospitalization.

- prolong the duration of hospitalization.
- cause persistent or significant disability.
- result in congenital anomalies or birth defects.
- require medical or surgical intervention to prevent permanent damage

Section 5: Statistical analysis

Patient Characteristics and Baseline Comparisons

Basic characteristics are described using mean and standard deviation (SD) or median and range, frequency and percentages.

Primary and Secondary Endpoint Analysis

Descriptive analysis is performed using mean, SD or median and range, frequency and percentages. The efficacy of the treatment is assessed by comparing the mean/median value of each parameter among visits, using the Paired Sample T-test or the nonparametric equivalent, Wilcoxon test. The statistical significance level is defined as $p < 0.05$.

Safety Analysis

All adverse events and adverse drug reactions will be recorded in the patient's medical file as well as in the designated section of the CRF. They will be classified based on severity, relevance, and relation to the treatment used in the study, and in accordance with the investigator's criteria and the guidelines outlined below.

Classification of adverse events based on severity:

Adverse events will be classified according to their severity into three categories: mild [1], moderate [2], and severe [3], based on the following definitions:

Mild: Any reaction, sign, or symptom that the individual can recognize but does not influence performance or functioning.

Moderate: Any reaction, sign, or symptom(s) of a sufficient severity to make the subject uncomfortable.

Performance of daily activities is influenced. This may require medical intervention.

Severe: Any reaction, sign, or symptom(s) of a sufficient severity to cause the subject severe discomfort.

Performance of daily activities/functioning is compromised and causes disability and/or poses a specific risk to health. This usually requires medical intervention.

Note: Severe AEs are not necessarily serious unless one of the serious outcomes has occurred.

List and describe each primary and secondary outcome including details of: methods used for assumptions to be checked for statistical methods

For t-test, normality of distributions will be assessed using the Shapiro-Wilk test.

Missing Data

No imputation will be done.

Covariate Adjustment

No covariate adjustment will be done.

Statistical Software

The analysis will be carried out using SPSS software.

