- Measurement of submental fat diameter
- Reporting and recording adverse events
- Evaluation the patient satisfaction

Visit 6 (20 weeks±4 days) (In subjectswith 3 injections):

- Digital AP and lateral photography of the patient's neck
- Grading of submental fat based on SMF
- Measurement of submental fat diameter
- Reporting and recording adverse events
- Evaluation the patient satisfaction

Participants:

This study will be conducted in 20 eligible participants.

Early Termination Policy: The decision to terminate the study early, due to safety concerns or to protect patient health, will be made by the Principal Investigator (PI) or the sponsor, with mutual agreement from both parties.

Withdrawal of Subjects

- The patients were allowed and free to refuse to cooperate with the study and follow-up whenever they want, but the researchers try to collect the maximum information, including the reasons for leaving the study and, if possible, the final results of the treatment.
- If a patient missed 2 or more consecutively scheduled visits, he/she was dismissed from the study.
- Occurrence of any of the exclusion criteria
- Occurrence of serious adverse event (SAE).

Data Collection

All required data will be recorded on the (paper) CRFs for this study, which will be designed and provided by PI. The reason for any missing data will be explained. All entries must be in permanent, blue ink. Errors will have single lines drawn through them with the correct data, recorder's initials, and date entered above the error. All errors must remain legible. Erasure or obliteration of errors in the CRF or other permanent study records are strictly prohibited.

Statistical analysis:

For statistical analysis, we performed descriptive statistics (mean, standard deviation or median and range, frequency and percentages). The efficacy of the treatment was assessed by comparing the mean/median value of each parameter among visits, using the Paired Sample T-test or the nonparametric equivalent, Wilcoxon test. SPSS 24 statistical software was used for data analysis. The statistical significance level was defined as $p<0.05$.

Adverse Events

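### The primary endpoint is a yes/no response at two visits, but efficacy is assessed by a test of shift in grade; the response rate has no deciding visit, interval or stated denominator

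*SAP*

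**What the plan says.** SAP Section 4 (Primary Endpoint) defines the outcome as "At least one-grade improvement in standard grading of submental fat (SMF) evaluated at 4 and 12 weeks after the last injection". The protocol's Primary Endpoint uses the same wording. This is a yes/no outcome per patient at two time points. Neither document says which time point decides, or whether response is needed at one or at both.

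SAP Section 5 (Primary and Secondary Endpoint Analysis) covers all endpoints in three sentences:

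- The first is descriptive: "Descriptive analysis is performed using mean, SD or median and range, frequency and percentages".
- The second says that efficacy is "assessed by comparing the mean/median value of each parameter among visits, using the Paired Sample T-test or the nonparametric equivalent, Wilcoxon test".
- The third sets significance at p<0.05.

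The protocol's Statistical analysis section gives the same method, "comparing the mean/median value of each parameter among visits". Neither document mentions a confidence interval, a test of a proportion, a reference rate or a success criterion.

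Three other statements bear on the point:

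- **Sample size:** "This study will be conducted in 20 eligible participants", with no derivation.
- **Missing data:** "No imputation will be done".
- **Leavers (Withdrawal of Subjects):** researchers try to collect, "if possible, the final results of the treatment".

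No analysis population is defined.

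**The concern.** The endpoint and the efficacy assessment answer different questions. The endpoint asks what share of patients improved by a grade or more. The paired test asks whether grades shifted between visits. The shift question matches the first secondary objective, on SMF grading, better than it matches the primary endpoint.

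With no control group, some improvers and few or no patients getting worse are enough to make a paired test significant, even when improvers are a minority. A reader given that p-value as the efficacy result would not learn how precisely the responder rate is known from 20 patients. With two visits and no rule between them, the plan also leaves open which rate is the primary result.

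**Working it through.** **Inputs.** n=20 (SAP, Sample size). Responder means at least one grade better (SAP, Primary Endpoint). Significance at 0.05 (SAP Section 5), taken as two-sided because the documents do not say. The patterns of change are assumptions for illustration. The plan gives no figure to reproduce, because the sample size comes without effect size, reference rate, power or dropout.

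**Formulas.** Unchanged patients drop out of the signed-rank test. With k improvers and w worse, all by one grade:

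- exact two-sided p = 2 × P(Binomial(k+w, ½) ≤ w); with w=0 this is 2/2^k, whatever the sizes of the improvements
- asymptotic, tie-corrected: Z = (k−w)/√(k+w)
- Clopper-Pearson 95% CI for x/n: the 2.5% quantile of Beta(x, n−x+1) to the 97.5% quantile of Beta(x+1, n−x)

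**Nobody worse.**

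- k=5: exact p = 2/32 = 0.0625.
- k=6: exact p = 2/64 = 0.031. Asymptotic Z = √6 = 2.449, p=0.014. Over all mixes of one- to four-grade improvements the asymptotic p runs from 0.014 to 0.027. So 6 of 20 is significant by either Wilcoxon version. The rate is 30% (CI 11.9% to 54.3%), and 14 of 20 patients missed the endpoint. The median change is 0, and it stays 0 up to 9 responders.
- k=4, one-grade changes: asymptotic Z = 2, p=0.0455; exact p = 2/16 = 0.125. At this margin the result depends on which Wilcoxon p-value is used, and the plan does not say.

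**One patient worse by one grade, one-grade changes only.**

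| Improvers | Exact p | Asymptotic p |
|---|---|---|
| 6 | 16/128 = 0.125 | 0.059 (Z = 5/√7) |
| 7 | 18/256 = 0.070 | 0.034 (Z = 6/√8) |
| 8 | 20/512 = 0.039 | 0.020 (Z = 7/√9) |

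The threshold moves to 7 improvers by the asymptotic test and to 8 (40%, CI 19.1% to 63.9%) by the exact test. Both are still a minority of 20.

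**Which branch of the plan applies.** The SAP requires a Shapiro-Wilk check before the t-test. Applied to the paired differences, it rejects normality in every threshold case above (p<0.001), so these cases go to Wilcoxon. The SAP does not say whether the check is on differences or on each visit's values. I therefore rest nothing on t-test p-values.

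**At a high response rate.** The protocol's Introduction cites 70% with one grade of improvement; this is background, not a design assumption. 14/20 with nobody worse gives exact p = 2/2^14 = 0.0001, so the test and the endpoint agree. The exact CI is 45.7% to 88.1%. At 10/20 it is 27.2% to 72.8%, a width of 45.6 points.

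**Denominator (secondary point).** The documents give no dropout figure, so assume 0 to 4 missing grades. Ten responders are then:

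- 10/20 = 50.0% (27.2% to 72.8%)
- 10/18 = 55.6% (30.8% to 78.5%)
- 10/16 = 62.5% (35.4% to 84.8%)

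**The case against.** The strongest case for the plan has five parts.

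1. **The scale is tested and the rate is reported.** SMF grade is presumably one of the parameters compared, and percentages and medians are planned in the same section. A reader would probably see 6/20 and a median change of 0 beside the p-value. This stands: the responder rate is not absent from the plan. But it carries no interval or denominator and plays no part in the sentence on how efficacy is assessed.
2. **A paired test is the ordinary inference for a before-after study, and there is no reference rate to test a proportion against.** This also stands. It is a reason to estimate the proportion with an interval, not a reason to let a different quantity carry the efficacy assessment.
3. **The conflict needs a low response rate.** It does, and it depends on how many patients worsen. With 6 improvers and one worse (one-grade changes), neither Wilcoxon version reaches 0.05. At 14/20 there is no conflict. Only the missing interval, visit and denominator apply at every response rate.
4. **Any reader can compute the interval from x/20.** True if the denominator is known, but the plan does not state it.
5. **Both visits are prespecified.** Reporting only the better one would depart from the text. A reader might infer that the sponsor would select the favourable visit. The documents do not support that; they only fail to rule it out.

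**Conclusion.** The point holds as a gap between endpoint and analysis that should be fixed. The only stated efficacy assessment does not address the responder rate, and that rate lacks a deciding visit, an interval and a denominator. With n=20 the efficacy p-value can fall below 0.05 at 30% response if nobody worsens. If one patient worsens by one grade, that takes 35% (asymptotic) to 40% (exact). These figures assume two-sided testing and the stated patterns of change; they locate thresholds and predict nothing.

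A reader might infer that the plan would declare success with most patients unimproved. The documents do not go that far: they set no success criterion, and they do plan to report percentages. A reader might also cite t-test p-values at still lower response rates. On the natural reading of the Shapiro-Wilk check, that test would not be used there.

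**What to change.** In SAP Section 5 and the protocol's Statistical analysis section:

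- Make the primary analysis the number and percentage of treated subjects with at least a one-grade SMF improvement at one named visit, with an exact Clopper-Pearson 95% CI. Twelve weeks after the last injection is one candidate, since it matches the 3-month follow-up in the inclusion criteria. In that case report the 4-week rate as secondary.
- State the denominator as all treated subjects, with a missing grade counted as non-response. Amend the missing-data sentence to say so, and give the observed-case rate as a sensitivity analysis.
- Base the efficacy wording on this estimate and interval. Keep the paired Wilcoxon on SMF grade (exact p-value stated) and the paired test on caliper diameter as supportive.
- If data have already been seen, label the change and the choice of visit as post hoc. The protocol's analysis paragraph is in the past tense, but the SAP is dated before the ethics approval, so the documents do not settle this.

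**Cost.** One SAP paragraph, the missing-data sentence and the matching protocol text. No new patients, visits or measurements are needed, because the grades are already scheduled. The efficacy statement becomes less favourable than a p-value against baseline, and counting missing grades as non-response can only lower the rate. The interval gives precision only; it does not supply a success criterion or replace a control group.
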